11.3.2.2 Proteogenomic Analysis of Tumor Biopsies (DNA, RNA and Proteomics)

This protocol aims to evaluate the kinome and phosphoproteome of metastatic TNBC. The analysis pipeline includes quantitative tandem mass tag (TMT)-based proteomics and phosphoproteomics, kinase inhibitor profiling (KiP)-based kinomics, tumor/normal exome sequencing, and RNA sequencing [9]. For participants with accessible disease, pre-treatment, on-treatment, and progression biopsies will be requested for proteogenomic profiling. We aim to examine signaling perturbations in response to treatment as well as the influence of tumor PTPN12 status on the kinome. In the event of clinical trial success, we will build a kinome profile of responding versus non-responding tumors.

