16. STATISTICAL CONSIDERATIONS

16.1 Study Design

This phase 2 biomarker-stratified study employs a modified optimal Simon two stage design. The decision rule, based on an adaptation of the approach of Jones and Holgren[1], is detailed below.

The primary endpoint is PFS24, where the success is defined as being alive and progression-free at 24 weeks after initiation of study treatment.

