16.2 Decision Rule(s)

The general flow and decision points are illustrated in Figure 4.

[figure not shown]

Figure 4. Adapted Phase 2 Design.

In Stage 1, the study will separately enroll seven PFS24 evaluable participants each in the PTPN12*high/normal* and PTPN12*low* cohorts. If there are no PFS24 events in the PTPN12*high/normal* cohort, enrollment to that stratum will close. If there is at least one PFS24 event observed in the PTPN12*high/normal* cohort, then, in Stage 2, the previously accrued PTPN12*low* and PTPN12*high/normal* cases will be combined into a single cohort, and the study will enroll additional cases, regardless of biomarker status, up to a total of 25 participants. At the end of the trial, three or more PFS24 events will be required to deem the therapy a success.

If there is no PFS24 event in the PTPN12*high/normal* cohort during Stage 1, the PTPN12*low* cohort will continue to accrue to 7 participants. If there are no PFS24 events in the PTPN12*low* cohort, enrollment to that stratum will close, and the trial will close. If there is at least one PFS24 event, then, in Stage 2, the study will accrue up to a total of 15 PFS24-evaluable PTPN12*low* participants. At the end of the trial, two or more PFS24 events will be required to deem the therapy a success, with PTPN12*low* status as a biomarker of benefit. Extensive simulations

indicate that operating characteristics of the proposed design perform as expected and are independent of the frequency of PTPN12*low* status.

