16.5.3 Exploratory Endpoints and Analysis

CTCs, CTC PTPN12 expression and ctDNA will be assessed longitudinally and will be correlated with baseline PTPN12 expression, to determine whether baseline CTCs can be used to assess PTPN12 status, to determine whether CTCs and ctDNA are predictive of response and/or PFS24. As appropriate, general linear mixed models will be used to model CTC and/or ctDNA trajectories. Exploratorily, phosphoproteomics will be examined before and after treatment to identify differentially expressed phosphoproteins due to treatment and baseline levels or changes in the phosphoproteome that might be predictive of clinical benefit. Tumor kinase profiling will be examined to identify differential kinase activity. Similarly, immune biomarkers will be examined to identify baseline differences or differential changes that might indicate the effect of immunocomponents on response. Data will be summarized descriptively with means and/or medians and 95% confidence intervals. False discovery methods will be employed to avoid multiple comparison issues with these higher dimensional data.

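### Outcome-linked biomarker analyses name only categorical outcomes, so a small trial forgoes power that progression time, already collected, would give

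*Combined protocol and SAP*

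**What the plan says.** - Section 16.5.3 will assess CTCs and ctDNA over time "to determine whether CTCs and ctDNA are predictive of response and/or PFS24". It seeks baseline levels or "changes in the phosphoproteome that might be predictive of clinical benefit", and examines immune markers for their bearing on response.
- Section 11.3.2.2 adds "In the event of clinical trial success, we will build a kinome profile of responding versus non-responding tumors".
- On multiplicity, section 16.5.3 says "False discovery methods will be employed to avoid multiple comparison issues with these higher dimensional data". It gives no procedure, error level, number of tests or expected number of samples.
- PFS24 is binary, "where the success is defined as being alive and progression-free at 24 weeks after initiation of study treatment" (section 16.1). Under section 16.2 the unselected path, with up to 25 participants, needs "three or more PFS24 events will be required to deem the therapy a success". The PTPN12-low path, with up to 15, needs "two or more PFS24 events will be required to deem the therapy a success".
- Richer outcomes exist. TTP is a secondary endpoint (3.2.1, 16.5.2), PFS is defined as a time (12.4.6), and target-lesion sums are recorded at baseline and at each assessment (12.3.1.2 to 12.3.1.4), every two 28-day cycles (section 8, note 5). Section 16.5.3 links no biomarker to any of them. Its mixed models describe marker trajectories, not outcome.

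**The concern.** With 15 to 25 participants, a split at 24 weeks treats someone who progresses at the first scan like someone who progresses just before week 24, and someone who progresses soon after week 24 like someone who stays progression-free for a year. If only two or three participants are on one side of the split, a real marker association can easily be missed. These analyses are meant to guide the choice of markers for later studies, so a miss has a cost even though no decision in this trial rests on them.

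**Working it through.** **1. The plan's own figures.**
- PTPN12-low (continue on at least 1 of 7, succeed on at least 2 of 15, rate 30%): Σ(i=1..7) Bin(i; 7, 0.30) × P(Y ≥ 2−i), Y ~ Bin(8, 0.30) = 0.903 (stated 90%).
- Unselected (at least 1 of 7 in the high/normal cohort, then at least 3 of 25, rate 25%): Σ(i=1..7) Bin(i; 7, 0.25) × P(Y ≥ 3−i), Y ~ Bin(18, 0.25) = 0.852 (stated 85%).

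Both reproduce.

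**2. How many successes a successful trial supplies.**
- Unconditional expectations: 15 × 0.30 = 4.5 and 25 × 0.25 = 6.25. Means given success: 4.7 and 6.6.
- Exactly 2/15 given success: (105 − 28) × 0.30² × 0.70¹³ / 0.903 = 7%. Exactly 3/15: (455 − 56) × 0.30³ × 0.70¹² / 0.903 = 17%.
- Exactly 3/25 given success: (2300 − 816) × 0.25³ × 0.75²² / 0.852 = 5%.

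So 2 or 3 is the floor, and 4 to 7 is typical.

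**3. Information kept by the 24-week split.** For exponential times under proportional hazards, the split keeps S(ln S)²/(1−S) of the information in a fully observed time, where S is the 24-week rate.
- S = 0.12: 0.61. S = 2/15: 0.62. S = 0.25: 0.64.
- S = 0.03 (the unacceptable rate): 0.38.

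The loss is about 35-40% at plausible rates.

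**4. Power for one marker.** Assumptions, none given in the documents: normally distributed marker, hazard ratio 2 per SD, exponential times, progression recorded on an 8-week scan grid (2 × 28 days), everyone followed to progression. Binary outcome: Mann-Whitney test. Time: Cox score test with tie-corrected variance. 4,000 simulations per cell.

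| Successes | Outcome | p ≤ 0.05 | p ≤ 0.05/17 | p ≤ 0.0001 |
|---|---|---|---|---|
| 2/15 | binary | 21% | 0% | 0% |
| 2/15 | time | 49% | 6% | 0% |
| 3/25 | binary | 46% | 6% | 0% |
| 3/25 | time | 76% | 29% | 2% |
| 6/25 | binary | 54% | 14% | 1% |
| 6/25 | time | 79% | 35% | 4% |

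A separately programmed check at the same hazard ratio gave smaller gains at 5%: 19% to 35% (2/15), 36% to 55% (3/25) and 52% to 67% (6/25). I quote the range across both.

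Tie handling matters. On the same 8-week grid, a Cox score test without the tie correction rejected only 0.6% of the time under the null at 3/25. At hazard ratio 2 its power was 32% at 3/25 and 11% at 2/15, below the binary test.

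**5. False-discovery threshold.** Table 1 lists 17 markers. At an assumed 5% level, the first-rank Benjamini-Hochberg threshold is 0.05/17 = 0.0029. The smallest two-sided exact rank p is 2/C(n,k):
- 2/15: 2/105 = 0.019, not reachable by a single marker.
- 3/15: 2/455 = 0.0044, not reachable.
- 4/15: 2/1365 = 0.0015, reachable.
- 3/25: 2/2300 = 0.00087, reachable.

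By step 2, the floor binds in about 7% + 17% = 24% of successful PTPN12-low trials at the 30% alternative, and not on the unselected path.

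**The case against.** The strongest reply is that this is exploratory work, summarised descriptively, that drives no trial decision. Section 4.2 itself warns that small numbers limit the immune microenvironment results. That is fair on severity, but a small sample is a reason to prefer the more efficient outcome.

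Several stronger readings are tempting, and the documents do not support them.
- *False-discovery control cannot be met.* It holds at any sample size; what falls is power. The floor in step 5 also depends on a rank test, a 5% level and 17 tests, none of which section 16.5.3 specifies. Parametric tests have no such floor.
- *Most of the information is discarded.* That is so only near the 3% unacceptable rate.
- *Every outcome comparison is 2 against 13.* The 2-or-3 floor applies to PFS24 alone. The decision rule does not set response counts, and clinical benefit includes any stable disease (3.2.3). RECIST response also has ordered categories, and section 16.5.3 does not say that it will be dichotomised.
- *The programme could not answer objectives 3.3.1 to 3.3.4.* Before/after phosphoproteomics, CTC versus tissue PTPN12, paired microenvironment comparisons and marker trajectories need no clinical outcome.

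It may also be objected that changing the outcome cannot overcome the sample size or the optional biopsies (section 8, note 8). For large screens this stands: at p ≤ 0.0001 and hazard ratio 2, power is at most 4% with progression time.

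Making the kinome profile conditional on trial success is a separate, debatable choice. A failed trial may have almost no responders, and the rest of section 11.3.2.2 is unconditional. This point does not rest on it.

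**Conclusion.** The point holds as a matter of efficiency. The outcome-linked biomarker analyses name only categorical outcomes while better ones are already collected. In the simulations, progression time adds about 15 to 30 percentage points of single-marker power at two-sided 5% (2/15: 16 to 28; 3/25: 19 to 30; 6/25: 15 to 25). The gain therefore does not depend on the trial ending at its minimum success count. For a 17-marker panel it is useful at 3/25 (6% to 29%) and small at 2/15 (0% to 6%).

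These sizes rest on an assumed hazard ratio of 2 per SD, proportional hazards, full follow-up to progression and tie-corrected tests. Censoring or fewer biopsied participants would lower power. I give no power figure for percentage change in diameters: PFS24 also turns on new lesions, non-target progression and death, so a simulation that equates success with the greatest shrinkage would flatter the comparison. This is a cheap improvement to exploratory analyses and does not bear on the primary decision rule.

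**What to change.** In section 16.5.3, and for any outcome comparison in section 11.3.2.2:
- Make PFS time the main outcome for single-marker and small-panel analyses, by Cox model or concordance, in all participants. Specify a method that suits heavily tied scan dates.
- For changes measured on treatment, start the clock at the later sample, so that remaining progression-free long enough to be sampled is not counted as benefit.
- Add best percentage change in sum of diameters, by rank correlation, for participants with measurable disease.
- Keep response, PFS24 and clinical-benefit comparisons as secondary description.
- State the false-discovery procedure and level, the list of tests and the expected number of samples. Report screens of thousands of phosphoproteins as hypothesis-generating.

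The cost is wording only, with no new data. Participants without measurable disease (bone-only disease is eligible under 5.1.2 but non-measurable under 12.1.5), and those with no post-baseline scan, contribute only to the PFS-time analysis. Analyses that do not use outcome are unaffected.

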16.6 Reporting and Exclusions

All PFS-evaluable participants will be included in analyses of the primary and secondary outcomes in their assigned group (modified-ITT population). All participants who receive any study treatment will be considered evaluable for the safety analysis (safety population).

All registered participants will be accounted for. Participants withdrawn or considered ineligible before starting study treatment will be replaced. Participants withdrawn prior to completing the first cycle of study treatment or determined to be ineligible, will be considered inevaluable for PFS24 and will be replaced.

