5.1.12 Ability to understand and the willingness to give informed consent

5.2 Exclusion Criteria

- 5.2.1 Uncontrolled hypertension, defined as systolic blood pressure > 150 and/or diastolic blood pressure > 100 , on two or more occasions within 30 days prior to enrollment
- 5.2.2 Imaging suggestive of lymphangitic carcinomatosis in the lung, or use of home O₂
- 5.2.3 Untreated brain metastases
- 5.2.4 Women who are pregnant or nursing
- 5.2.5 Concurrent metastatic disease of another tumor type
- 5.2.6 Impairment of gastrointestinal (GI) function or GI disease that may significantly alter the absorption of sitravatinib
- 5.2.7 History of stroke, pulmonary embolus (PE), or myocardial infarction (MI)
- 5.2.8 Known proteinuria of ≥ 2 g urinary protein/24 h
- 5.2.9 HIV-positive participants
- 5.2.10 History of Hepatitis C or Hepatitis B infection
- 5.2.11 History of congestive heart failure (CHF), and/or LVEF $< 50\%$
- 5.2.12 Concurrent use of medications that prolong QTc (listed in Section 9, Table 11) . These medications need to be discontinued at least 2 weeks prior to starting study treatment.
- 5.2.13 Concurrent medical condition that, in the sole judgment of the principal investigator, would make the patient inappropriate for trial participation

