8. STUDY CALENDAR

Test/Procedure	Pre-Study ¹	C1D1	C1D14	Subsequent Cycles Day 1	End of Treatment	Safety Follow-Up ¹¹	Survival Follow-Up
Informed Consent	X						
Participant Demographics	X						
CLINICAL EVALUATIONS							
History and Physical Exam	X	X	X	X	X		
Height	X						
Vital signs and weight	X	X	X	X	X		
Performance Status	X	X	X	X	X		
LABORATORY/RADIOLOGIC EVALUATIONS							
CBC/differential	X		X	X	X		
Comprehensive Metabolic Panel	X		X	X	X		
TSH	X		X	^{X⁴} (odd cycles)	X		
Urine Protein/Creatinine Ratio	X		X	^{X⁴} (odd cycles)	X		
Pregnancy test	^{X²}						
Tumor Assessments	X			^{X⁵}	X		
Echocardiogram	X			^{X⁶}			
TREATMENT DISPENSATION							
Sitravatinib		X		X			
CORRELATIVE							
ctDNA collection	X		X	^{X⁷}	X		
CTC collection	X		X	^{X⁷}	X		
Tumor/Tissue Biopsy ⁸	^{X¹⁰}		^{X³}		X		
Archival tissue	^{X⁹}						
ADDITIONAL INFORMATION							
Concomitant Medications	X		X	X	X	X	
Adverse Events/Toxicity Assessment				X	X	X	
Compliance Assessment				X	X		
Assess vital status							^{X¹²}

NOTE: The schedule may be modified +/- 3 days due to scheduling delays or conflicts (e.g. holidays, inclement weather, vacations, etc.)

1. All pre-study assessments, with the exception of the informed consent, must be performed within 28 days prior to starting study treatment, unless otherwise indicated.
2. Urine or serum pregnancy test is acceptable; to be performed for women of child-bearing potential only
3. May be performed any time between Cycle 1, Day 14 and Cycle 3, Day 14
4. To be performed prior to dosing on C3D1, then prior to dosing on Day 1 of every odd-numbered cycle thereafter (e.g., C5D1, C7D1, etc.)
5. Clinical and radiological tumor assessments will be performed by CT, PET or MRI scan at baseline and then every 2 cycles (i.e., within 7 days prior to Cycles 3, 5, 7, and 9) until disease progression. The same testing modality should be used for each evaluation. Responses of CR or PR should be confirmed with a second assessment no earlier than 4 weeks, but no later than the next scheduled scan, per protocol. Brain MRI and bone scan should be performed if clinically indicated (e.g., participants with known history of bone or brain mets). Results must be reviewed for each scan prior to dosing at next cycle
6. To be performed within 7 days prior to C4D1. Further echocardiograms may be performed as clinically indicated.
7. To be collected on C2D1, C3D1, then on Day 1 of each odd-numbered cycle thereafter (e.g., C5D1, C7D1, etc.)

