12.4.7 Response Review

There is no independent or central review of the radiology assessments planned for this trial. It is the responsibility of each participating site's Principal Investigator to ensure that tumor assessments are reported per the RECIST 1.1 criteria outlined above. The Principal Investigator (or designee) may choose to review select cases.

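### Section 16.6 drops and replaces treated participants found ineligible, with no explicit cut-off and no tie to pre-treatment data, so known PFS24 failures could be removed selectively

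*Combined protocol and SAP*

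**What the plan says.** Section 16.6 has two replacement sentences. The first covers the period before dosing: "Participants withdrawn or considered ineligible before starting study treatment will be replaced". The second begins "Participants withdrawn prior to completing the first cycle of study treatment" and continues "or determined to be ineligible, will be considered inevaluable for PFS24 and will be replaced". Since the first sentence already deals with ineligibility found before dosing, the ineligibility limb of the second must reach people who have started sitravatinib.

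The same section limits primary and secondary analyses to PFS-evaluable participants, so anyone excluded this way leaves every efficacy analysis. All treated participants are kept only for safety.

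Section 16.1 defines the endpoint by success, "where the success is defined as being alive and progression-free at 24 weeks after initiation of study treatment". In Section 16.2 a PFS24 event therefore means a success. The gates there are at least 1 of 7 in Stage 1, then at least 3 of 25 (pooled) or at least 2 of 15 (PTPN12-low).

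Other relevant text:

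- Section 6: eligibility is verified before enrollment.
- Exclusion 5.2.13: rests on the principal investigator's sole judgment.
- Section 12.4.7: "There is no independent or central review of the radiology assessments planned for this trial".
- Study calendar, footnote 5: "Brain MRI and bone scan should be performed if clinically indicated", with a known history of bone or brain metastases given as an example.
- Exclusion 5.2.3: "Untreated brain metastases".

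**The concern.** A rule that removes treated participants from the primary denominator is safe only if it cannot respond to outcome. Here the people who judge eligibility also know how the participant is doing, and a poor course is the usual prompt for a second look at the entry criteria. Nothing requires the finding to rest on pre-treatment data or to be made before the outcome is known.

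An example follows from the protocol's own text. Brain MRI at baseline is not universal. A brain lesion first seen on treatment is a new lesion, hence progression under Sections 12.4.2.3 and 12.4.5, and a PFS24 failure. The same lesion could be argued to have been present and untreated at entry, which breaches 5.2.3. Section 16.6 would then delete and replace the participant. The plan does not say which reading governs the denominator.

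The result is compared with a fixed rate of 3%, and the decision thresholds are one, two or three successes. Swapping known failures for fresh participants raises the chance of passing while the reported denominator looks unchanged.

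**Working it through.** **Inputs.** Sections 16.2 and 16.3: Stage 1 of 7 per cohort; final sizes 15 and 25; success thresholds 2 and 3; unacceptable rate 3%; target rates 30% (PTPN12-low) and 25% (unselected); one-tailed alpha 0.075.

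**Rule.** Let h and l be the Stage 1 successes in the high/normal and low cohorts, each Bin(7, p).

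- Pooled route: h ≥ 1, then h + l + Bin(11, p) ≥ 3.
- Low route: h = 0 and l ≥ 1, then l + Bin(8, p) ≥ 2.

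The routes exclude each other, so their probabilities add.

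**The plan's own figures.** The low path alone (≥1 of 7, then ≥2 of 15) has power 0.9034 at 30%, against a stated 90%. The unselected path (≥1 of 7 high/normal, then ≥3 of 25) has power 0.8525 at 25%, against a stated 85%. Both reproduce.

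**Error at 3% with no selective exclusion.** The pooled route gives 0.0253. The low path alone gives 0.0549. Within the whole trial it needs h = 0, so it contributes 0.97^7 × 0.0549 = 0.8080 × 0.0549 = 0.0444. The total is 0.0696 (from unrounded terms).

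**Replacing k known failures.** Dropping a known failure and enrolling a substitute adds one draw with the thresholds unchanged, so 7 becomes 7 + k in that cohort. For one Stage 1 gate, the pass rate at 3% goes from 1 − 0.97^7 = 0.192 to 1 − 0.97^8 = 0.216. For the whole trial at 3%:

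| Known failures replaced | Pooled route | Low route | Total |
|---|---|---|---|
| None | 0.0253 | 0.0444 | 0.0696 |
| One, Stage 1 high/normal | 0.0297 | 0.0430 | 0.0727 |
| One, Stage 2 | 0.0272 | 0.0477 | 0.0749 |
| One, Stage 1 low | 0.0272 | 0.0519 | 0.0792 |
| One in each Stage 1 cohort | 0.0319 | 0.0504 | 0.0823 |
| One in each Stage 1 cohort and one in Stage 2 | 0.0342 | 0.0539 | 0.0881 |
| Two in each Stage 1 cohort | 0.0393 | 0.0562 | 0.0955 |

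Totals use unrounded terms. A simulation of one replacement in each Stage 1 cohort gave 0.0822.

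**The PTPN12-low comparison alone.** Replacing one, two or three Stage 1 low failures moves 0.0549 to 0.0643, 0.0739 and 0.0838.

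**As a fraction of failures.** If a fraction r of all failures is replaced and every success is kept, the effective rate is p / (p + (1 − p)(1 − r)). At p = 0.03 and r = 10% this is 0.03 / (0.03 + 0.97 × 0.90) = 0.0332, and the total error is 0.0845. At r = 20% and 30% the effective rates are 0.0372 and 0.0423, with errors 0.1046 and 0.1323. For 25 counted participants, the number deleted is 25 × (1 − effective rate) × r / (1 − r): about 2.7, 6.0 and 10.3.

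**The case against.** **The timing phrase can be read to cover both limbs.** If completing Cycle 1 also limits the ineligibility limb, exclusion months into treatment is ruled out. This reading is available, so it should not be stated as fact that the plan permits exclusion at any time. It is the less natural reading, however, and it would still allow a progression or death in Cycle 1 to be removed. Section 12.1.2 expressly keeps participants with objective progression in Cycle 1 evaluable for response; Section 16.6 has no such protection for PFS24.

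**Safeguards exist.** Eligibility is checked before enrollment, all registered participants must be accounted for, and an external DSMB sees accrual and response data at least annually. These make late findings less common and more visible. None sets a cut-off or restores an excluded participant to the efficacy analysis.

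**The protocol already classes a new lesion as progression.** True, so a sentence repeating that would add little. Those sections define response. They do not say that a progression stays in the denominator once the participant is also called ineligible.

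**Other routes a reader might infer.** Lymphangitic spread (5.2.2) looks parallel to the brain example, but it is an imaging criterion and baseline tumor assessment is mandatory, so the documents show no route to late discovery. Deleting a lone success could also close a gate (exactly 1 of 7 has probability 31.2% at a 25% rate), but nothing in the documents suggests why a success would prompt an eligibility review. Neither supports the point.

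**Conclusion.** The concern holds as a flaw in the definition of the primary denominator. Section 16.6 excludes and replaces treated participants for ineligibility without an explicit cut-off or a pre-treatment-data requirement, and no all-treated efficacy analysis is planned.

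The likely effect is modest. If removal depends on outcome, the whole-trial chance of a false success at 3% moves from 0.0696 to between 0.0727 and 0.0792 for one replaced failure, 0.0823 for one in each Stage 1 cohort and 0.0955 for two in each. If removal is unrelated to outcome, the error is unchanged. The documents give no late-ineligibility rate, so the counts are assumptions shown as a range.

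Two stronger conclusions are not supported:

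- A reader might infer error of 0.10 to 0.13 from replacing 20% to 30% of failures. In a trial filled to 25 that means about 6 to 10 deleted failures with no successes deleted, and nothing in the documents points to such numbers.
- A reader might infer that one replacement breaches the stated alpha. Section 16.3 attaches 0.075 to the PTPN12-low comparison, so using it as a whole-trial limit is an assumption. Even then only a Stage 1 low replacement (0.0792) exceeds it among the single-replacement cases. On the low comparison alone, two replaced Stage 1 failures still give 0.0739.

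**What to change.** Amend Section 16.6 as follows:

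- A treated participant may be excluded and replaced for ineligibility only if it is established from pre-treatment data and documented before the first post-baseline tumor assessment and before any progression, symptomatic deterioration or death. The second condition is needed because the first scheduled scan falls shortly before Cycle 3, and failures can occur earlier.
- All other treated participants found ineligible stay in the PFS24 denominator and are reported as eligibility deviations.
- PFS24 and the Section 16.2 decision rule are also reported in all treated participants, as a sensitivity analysis.

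The cost is a few sentences and one additional tabulation, with no change to sample size, procedures or treatment. With exclusion made independent of outcome, the design keeps its figures: power 0.903 and 0.852, and whole-trial error 0.0696. The downside is that an occasional truly ineligible participant stays in the denominator.
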